16. Sample(s) collected for analysis at central lab. The same sample will be used for BCMA (flow) and PD. On D8 only postdose PD assessment will be performed, if applicable (refer to footnote 18).
17. FISH testing at least for: t(4;14), t(14;16), 17p13del. FISH results from samples taken within 60 days prior to first dose are acceptable.
18. **Additional samples may be collected in some subjects (up to 6) for further exploration of PD.**
19. Archival tissue from up to 60 days prior to study is acceptable.
20. Collect sBCMA at C1D1 predose (within 30 minutes prior to SOI) and at EOI (± 5 minutes), C2D1 at predose (within 30 minutes prior to SOI) and at EOI (± 5 minutes).
21. Collect cytokines at predose (within 30 minutes prior to SOI) and EOI (± 5 min) (even when infusion is interrupted or halted) to assess allergic reaction
22. All ADA samples will be collected prior to each infusion
23. Flow cytometry performed central laboratory.
24. PK samples to be taken for both GSK2587916 and cys-mcMMAF measurement on C1D1, C2D1, C3D1, and C5D1 at predose (within 30 minutes prior to SOI) and at EOI (just before EOI).
25. Collect 1 PK sample at each subject's final visit.
26. Informed consent for optional genetics research should be obtained before collecting a sample.
27. Study drug administration ± 3 day window only.
28. Prophylaxis with prednisolone phosphate 1% or dexamethasone 0.1% 1 drop QID x 4 days starting 1 day prior to treatment
29. All participants should be followed for survival for 1 year from last subject last dose. and whether subsequent treatment for disease was given. Subject does not need to come in for visit. Participants who have completed treatment or the 3 month follow up visit (end of study) prior to amendment 5 will be reconsented for further follow up and survival status.
30. e-Diary to be completed at screening, then Days 1-7, 8, 15 of each treatment cycle. Upon implementation of the e-Diary, these assessments will be required.
31. OSDI and NEI-VFQ-25 to be administered during end of study treatment visit. Additional assessments for subjects who are experiencing corneal symptoms to be completed via telephone on a monthly basis for up to 1 year, or until resolution of symptoms (whichever comes first) during the follow-up period.
32. Exit interview to be performed within 21 days of end of study visit

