16.9. Appendix 9: Population Pharmacokinetic (PopPK) Analyses

16.9.1. Population Pharmacokinetic (PopPK) Dataset Specification

Any deviations between the dataset specification and the final dataset will be documented in the population pharmacokinetic analysis report.

General Description:

1. The type of variables should be either NUM or DATE/TIME unless specified otherwise
2. The dataset is sorted by ID, RTFDD, ANALN, ASCENDING EVID unless specified otherwise
3. The data items (columns) in the analysis-ready data file will be in the same order as follows.
4. Exclude observations with DTYPE=IMPUTE
5. Include PKFL=Y (applicable to all datasets)
6. Same rules are applied for other baseline covariates. Baseline rules are as follows:
 - Use baseline value as defined by Stats in the lab test datasets;
 - If not defined by Stats, set to measurement nearest to, but prior to, time of first dose
 - Only in cases where Day 1 measurement is not available, but screening measurement is, the screening values will be used.
7. 3 significant figures for all values.

Column Header	Data Item	Codes	Derivation/Comments	Source data set
C	Line number/exclusion identifier	Row Number STM DRM PFD	Set to line/row number unless one or more of the following conditions are met, then set to code: 
 • STM = If a PK sample was taken but the date and/or time of the sample is missing and cannot be derived • DRM= PK samples for which dosing records are missing • PFD=PK samples with CONC reported as NA/NR/NQ/BQL/missing at pre-dose in CYCLE =1 	derived
STUDY	Study ID		1 = BMA117159	adpc
SUBJID	Subject identifier from source data		SUBJID = SUBJID	adsl
ID	NONMEM subject identifier		Sequential subject identifier across studies after data is sorted by SUBJID. Starting with P	derived

Column Header	Data Item	Codes	Derivation/Comments	Source data set
AMT	Amount of GSK2857916 given (in mg)		AMT = ALTDOSE, where PARAMCD=ALTDOSE only on the dosing line. For all other lines use "."	adex
INFD	Infusion Duration (day)		(AENDTM-ASTDTM)/60/60/24 This value will only be used on the dosing line. For all other lines use "."	adex
INFH	Infusion Duration (h)		(AENDTM-ASTDTM)/60/60 This value will only be used on the dosing line. For all other lines use "."	adex

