RATED	Rate of infusion (mg/day)		RATED = AMT/INFD; where INFD is the infusion duration and is computed from start and stop time of infusion (in days) This value will only be used on the dosing line. For all other lines use "."	derived
RATEH	Rate of infusion (mg/h)		RATEH = AMT/INFH; where INFH is the infusion duration and is computed from start and stop time of infusion (in h) This value will only be used on the dosing line. For all other lines use "."	derived
RTFDD	Relative time from start of first infusion on study (day)		RTFDH=((ADTM-ASTDTM)/60/60/24)	adpc, adex
RTFDH	Relative time from start of first infusion on study (h)		RTFDD=((ADTM-ASTDTM)/60/60);	adpc, adex
RTLDD	Relative time from start of the most recent dose on study (day)		RTLDD = RTLDD/24	derived
RTLDDH	Relative time from start of the most recent dose on study (h)		AWNLRD = RTLDDH	adpc
NOMTLDD	Planned nominal time relative to start of most recent infusion (day)		NOMTLDDH/24	adpc
NOMTLDDH	Planned nominal time relative to start of most recent infusion (h)		Derive from PCTPT when (PCTPT = 'PRE-DOSE'), NOMTLDDH=0; when (PCTPT='DOSE'), NOMTLDDH =0; when (PCTPT = "30M POST START OF INFUSION (SOI)"), NOMTLDDH =0.5; when (PCTPT = "END OF INFUSION (EOI)"), NOMTLDDH =1; when (PCTPT = "1 HOUR POST-EOI"), NOMTLDDH =2; when (PCTPT = "3 HOURS POST-EOI"), NOMTLDDH =4; when (PCTPT = "8 HOURS POST-EOI"), NOMTLDDH =9; when (PCTPT = "24 HOURS POST-EOI"), NOMTLDDH =25; when (PCTPT = "7 DAYS POST-EOI"), NOMTLDDH =168; when (PCTPT = "14 DAYS POST-EOI"), NOMTLDDH	adpc

Column Header	Data Item	Codes	Derivation/Comments	Source data set
			=336; when (PCTPT ="END OF STUDY"), NOMTLDH =10000; otherwise NOMTLDH =.;	
CTIME	Clock time sample was obtained	Clock time (24 h) '00:00'	TIMEPART (EVENT) Format TIME5.	all dataset
DATE	Date of event (MM/DD/YYYY)		DATEPART (EVENT) Format DATE9.	all dataset
ANALN	Analyte	1= ADC(antibody-drug conjugate) 2= TOTALMAB(total antibody including complex) 3= MMAF(cys-mcMMAF)	This value will be used on all lines except for dosing record line where missing "." will be used. EXCLUDE MAB PARAMCD in (P1RES, P5RES, P7RES), assign ANALN =3, 1, 2 respectively	adpc
DV	Plasma concentration (ng/mL) of GSK2857916 (antibody-drug conjugate), total antibody (including complex) and cys-mcMMAF		If AVALC=NA/NR/NQ/BQL/missing, set DV= "." Else DV=AVAL When PARAMCD=P1RES, then DV=AVAL/1000 [Convert cys-mcMMAF from pg/mL to ng/mL precision (3 significant figures).For example, 0.111 pg/mL = 0.000111 ng/mL]	adpc

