16.9.2. Population Pharmacokinetic (PopPK) Methodology

The primary goal of this analysis is to characterize the population pharmacokinetics of GSK2857916 and associated analytes after intravenous administration of GSK2857916 in subjects with multiple myeloma. This analysis will be performed by CPMS and reported separately.

A summary of the planned population pharmacokinetic analyses is outlined below:

- Exploratory data analyses will be performed to understand the content of the analysis dataset with respect to the anticipated models, to search for extreme values and/or potential outliers, to examine the correlation between covariates, and to assess possible trends in the data.
- Drug concentration-time data will be subjected to nonlinear mixed effects modelling using appropriate validated software to develop a population PK model.
- Based on the preliminary analysis, log-transformed drug concentration data for GSK2857916 ADC will be subjected to analysis using a two-compartment IV infusion model parameterized using either clearances and distribution volumes, micro-constants or macro-constants (A, B, ALPHA and BETA), depending on parameters to be estimated. A similar approach may be used on the data from the three analytes (ADC, total antibody, and cys-mcMMAF) together.
- Inter-individual or between-subject variability (IIV or BSV) will be initially modeled using an exponential random effects model. Random effects for clearances and volumes or A and B and BETA will be incorporated, depending on model parameterization used. If the goodness-of-fit plots reveal potential biases in the random effects model, alternative random effects models may be considered.
- An additive error model on a log-transformed data scale reflecting an exponential error residual variability model will initially be used to describe the residual variability. If the goodness-of-fit plots reveal potential biases in the residual variability model, other residual error models will be considered as appropriate.
- Covariate analysis will be performed to explore measurable sources of PK variability. Different approaches may be evaluated for covariate model building including a step-wise process consisting of a forward and a backward selection procedure and/or a full-model approach. Some of the prospectively identified covariates are listed below:
 - Continuous covariates such as age, albumin, measures of body size (e.g., body weight, body surface area, body mass index, lean body mass);

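### The PopPK dataset rule of three significant figures exempts no column; read literally, it gives many later-cycle end-of-infusion samples the same cumulative time as the infusion start

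*SAP*

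**What the plan says.** SAP Section 16.9.1 opens with general rules for the population PK file. Item 7 reads "3 significant figures for all values" and lists no exception. Item 2 reads "The dataset is sorted by ID, RTFDD, ANALN, ASCENDING EVID unless specified otherwise", so RTFDD, the time in days since the start of the first infusion, orders the records. RTFDH is the same quantity in hours. Both are numeric and come from actual date-times. The file also holds time since the most recent dose, nominal time, and a clock time ("Clock time sample was obtained") with a separate date.

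Section 16.5.3 says that the file for the modelling group is built to this specification. In Section 16.9.2, "log-transformed drug concentration data for GSK2857916 ADC will be subjected to analysis using a two-compartment IV infusion model". For Part 2 myeloma, Section 16.2.3.1 (footnote 24) schedules PK "measurement on C1D1, C2D1, C3D1, and C5D1 at predose (within 30 minutes prior to SOI) and at EOI".

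**The concern.** Three significant figures is a relative precision. It suits a concentration, but not a clock that runs for months while the event of interest lasts one hour. Once cumulative time is large enough, the start and end of an infusion can no longer be told apart. A record that holds the peak concentration then sits where an infusion model predicts the pre-infusion level.

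Most scheduled peaks are exposed. Three of the four EOI samples per subject in Part 2 fall after Cycle 1, as do two of the three in Part 1 (Section 16.2.2.1, footnote 21). Population PK parameters in the expansion cohorts are a secondary endpoint (Section 2.2). The exposure-response datasets in Section 16.10.1 derive AUC as dose divided by individual clearance, so an error in clearance would pass inversely into AUC.

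**Working it through.** **Inputs from the SAP.** Infusion 60 min and cycle 21 days (Section 2.3); dosing window ±3 days (Section 16.2.3.1, footnote 27); PK sampling as above. The SAP gives no figure for the effect of rounding, so there is none to reproduce. Its own example of the precision holds: 0.111 pg/mL becomes 0.000111 ng/mL.

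**Step 1, planned times.** Cycle c starts at 21 × (c − 1) days, and EOI is 1/24 = 0.0417 day later.

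| Cycle | Days, start / EOI | At 3 figures | Hours, start / EOI | At 3 figures |
|---|---|---|---|---|
| 1 | 0 / 0.0417 | 0 / 0.0417 | 0 / 1 | 0 / 1 |
| 2 | 21 / 21.0417 | 21.0 / 21.0 | 504 / 505 | 504 / 505 |
| 3 | 42 / 42.0417 | 42.0 / 42.0 | 1008 / 1009 | 1010 / 1010 |
| 5 | 84 / 84.0417 | 84.0 / 84.0 | 2016 / 2017 | 2020 / 2020 |

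In days the collision begins at Cycle 2. In hours it begins at Cycle 3, once time passes 1000 h.

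**Step 2, actual times.** From day 10 to day 100 the grid is 0.1 day = 2.4 h. If the start falls anywhere on that grid with equal chance, a gap of 1 h is lost with probability 1 − 1/2.4 = 0.58. Simulation with starts spread over ±3 days gave 0.58 in Cycles 2, 3 and 5. The other 42% or so land one step, 2.4 h, after the start. In hours the share lost was at most 5% in Cycle 2, about 50% in Cycle 3 and about 90% in Cycle 5.

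**Step 3, columns that survive.** At EOI, time since last dose is 1.00 h or 0.0417 day, nominal time is 1 h, and clock time and date have fixed formats. None is harmed.

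**Step 4, consequence if a rounded column is the model time.** The SAP gives no PK values, so these are assumptions: CL 0.5, 0.9 and 1.5 L/day; V1 4 L; Q 0.7 L/day; V2 4 to 6 L; between-subject variability 30% on CL and 20% on V1; residual SD 0.25 on the log scale; 75 kg; 35 Part 1 and 40 Part 2 subjects. Data were simulated on the SAP's sampling times and fitted with a two-compartment mixed model on log concentrations, two random seeds per setting.

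| Model time | CL vs truth | Median AUC, estimated/true | Residual SD |
|---|---|---|---|
| Unrounded | −4% to +5% | 0.96 to 1.00 | 0.25 to 0.26 |
| RTFDD at 3 figures, actual times | −30% to −50% | 1.4 to 1.9 | 0.77 to 1.44 |
| RTFDD at 3 figures, planned times | −54% to −64% | 2.2 to 2.7 | 0.91 to 1.66 |

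With RTFDH at three figures, CL was 76% or more too low and many fits collapsed with CL near zero. That is best read as a failed fit, not as an estimate of bias.

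**Step 5, log columns.** A log concentration of 10 or more (about 22,026 ng/mL upwards) is rounded in steps of 0.1. The largest error is 0.05, and exp(0.05) = 1.05, so up to about 5%.

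**The case against.** The best defence is that nobody meant the rule for times. Item 7 follows an item on baseline values, and the only worked example of three-figure precision is a concentration. The time rows give plain date-time differences with no rounding. Taken literally, the rule would even round row numbers above 999. The specification lets departures be documented in the report, and Section 16.9.2 plans exploratory and goodness-of-fit checks. A residual SD three to seven times too large should be noticed.

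Much of this stands. It makes harm less likely, and it means that the bias may not be stated as an expected result. It does not correct the rule. Section 16.5.3 makes this text the build instruction. The deviation clause covers departures from the specification, whereas here the damage comes from following it.

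Two stronger readings are tempting and fail. A reader might infer that item 7 must be aimed at the non-concentration columns, because the concentration rows carry their own three-figure note. That note belongs only to the pg/mL to ng/mL conversion of cys-mcMMAF; ADC and total antibody have no such note and still need item 7. A reader might also infer that every EOI sample from Cycle 2 on collides. That holds only for planned times in days. Cycle 2 in hours stays distinct, and with actual times about four in ten EOI samples in days land 2.4 h after the start.

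**Conclusion.** The point holds as a defect of scope. As written, item 7 covers RTFDD and RTFDH, and the loss of the infusion interval follows by arithmetic from the SAP's own cycle and infusion lengths.

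The effect on clearance and AUC is conditional: the rule must be applied literally to the cumulative times, a rounded RTFDD or RTFDH must be the model time, and the poor fit must go uncorrected. The SAP does not name the model time column, so it does not support saying that clearance and AUC will be biased. If the conditions are met with RTFDD, the direction is consistent across all assumed settings (clearance low, AUC high). The size is material: an AUC ratio of about 1.4 to 1.9 with actual times, which are what the specification uses, and 2.2 to 2.7 with planned times. These sizes rest on assumed PK values and cohort sizes.

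Rounding of the log columns is a minor secondary point. Time since dose, infusion duration, dose and rate are not materially harmed by three figures.

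**What to change.** Reword item 7 so that three significant figures applies only to untransformed concentrations and covariates. State that RTFDD, RTFDH, identifiers and row numbers, and all log-transformed columns are kept at full precision, with at least four decimals for times in days and for logs. Four decimals in days is a step of 0.0001 × 1440 = 0.144 min, ample for a 60-minute infusion.

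The cost is one sentence in the dataset specification. No new data and no change of model are needed.

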16.9.2. Population Pharmacokinetic (PopPK) Methodology

The primary goal of this analysis is to characterize the population pharmacokinetics of GSK2857916 and associated analytes after intravenous administration of GSK2857916 in subjects with multiple myeloma. This analysis will be performed by CPMS and reported separately.

A summary of the planned population pharmacokinetic analyses is outlined below:

- Exploratory data analyses will be performed to understand the content of the analysis dataset with respect to the anticipated models, to search for extreme values and/or potential outliers, to examine the correlation between covariates, and to assess possible trends in the data.
- Drug concentration-time data will be subjected to nonlinear mixed effects modelling using appropriate validated software to develop a population PK model.
- Based on the preliminary analysis, log-transformed drug concentration data for GSK2857916 ADC will be subjected to analysis using a two-compartment IV infusion model parameterized using either clearances and distribution volumes, micro-constants or macro-constants (A, B, ALPHA and BETA), depending on parameters to be estimated. A similar approach may be used on the data from the three analytes (ADC, total antibody, and cys-mcMMAF) together.
- Inter-individual or between-subject variability (IIV or BSV) will be initially modeled using an exponential random effects model. Random effects for clearances and volumes or A and B and BETA will be incorporated, depending on model parameterization used. If the goodness-of-fit plots reveal potential biases in the random effects model, alternative random effects models may be considered.
- An additive error model on a log-transformed data scale reflecting an exponential error residual variability model will initially be used to describe the residual variability. If the goodness-of-fit plots reveal potential biases in the residual variability model, other residual error models will be considered as appropriate.
- Covariate analysis will be performed to explore measurable sources of PK variability. Different approaches may be evaluated for covariate model building including a step-wise process consisting of a forward and a backward selection procedure and/or a full-model approach. Some of the prospectively identified covariates are listed below:
 - Continuous covariates such as age, albumin, measures of body size (e.g., body weight, body surface area, body mass index, lean body mass);
 - Categorical covariates such as gender, race, disease status, immunogenicity status, and geographic region.
- Non-parametric bootstrapping may be performed to test model robustness. The model performance may be evaluated by performing predictive check.
- Individual *post hoc* estimated PK parameters will be summarized descriptively.
- Individual subject PK parameters and exposure measures for Cycle 1 will be estimated and documented for the purposes of any subsequent exposure-response (PK/PD) analyses.

Any analyses not described *a priori* but undertaken based on emerging data will be described in detail in the report.

Data handling considerations are summarized below:

- Drug concentration data which are below the lower limit of quantification, LLQ, (NQ or BLQ) are not reported as a numeric value. Such NQ observations will be either discarded or handled in a special way. When the frequency of NQ is small, the NQ values will be excluded, since discarding NQ values in this case introduces little bias [Beal, 2001]. In situations where there are a large percentage of NQ values, other strategies which may reduce estimation bias will be considered [Beal, 2001; Hing, 2001; Ahn, 2008]. The total number and percentage of NQ values will be calculated and the rationale for the method for handling these NQ values will be documented in the final report. In situations with large number of NQ values, the predictive performance of the model will be assessed to compare the agreement between observed versus predicted proportion of samples below the LLQ.
- Concentrations that are inconsistent pharmacokinetically with the drug concentration-time profile within an individual may be considered as outliers and subsequently excluded from the dataset or analysis. Visual inspection of individual and pooled data and weighted residuals during analysis may be used to identify such outliers. Any such exclusion will be reported and discussed in the analyses summary.
- Missing data will be handled in the following way:
- Subjects who withdrew from the study and did not provide any PK samples and do not have adequate sampling and/or covariate information will be excluded from the analysis.
- If dosing and/or sampling times are missing, the relevant concentrations may be excluded from the analysis dataset and summarized in an exclusion listing file. Alternatively, the nominal times of the respective doses and/or samples may be utilized.
- Imputations of any covariate value will only be performed if the variable is missing for less than 10% of the subjects. For continuous covariates, missing values for an individual subject will be imputed as the gender-specific median value for the study. Any changes to the imputation methods will be justified and documented. If the percentage of missing data is greater than 10%, the variable will only be evaluated in exploratory graphical displays and not in the population analyses. Subjects from race categories with an insufficient number for analysis (typically less than 10% of the subject population) may be re-grouped and/or defined as race “Other.”

16.10. Appendix 10: Pharmacokinetic / Pharmacodynamic Analyses

16.10.1. Pharmacokinetic / Pharmacodynamic Dataset Specification

Dataset specifications for exposure-response analyses of efficacy and of corneal toxicity are provided. Any deviations between the dataset specifications and the final datasets will be documented in the population pharmacokinetic analysis report.

For corneal toxicity

Column Header	Data Item	Codes	Derivation/Comments	Source data set
C	Line number/exclusion identifier	Row Number	Set to line/row number	adae
STUDY	Study ID		1 = BMA117159	adsl
SUBJID	Subject identifier from source data		SUBJID = SUBJID	adsl
ID	NONMEM subject identifier		Sequential subject identifier across studies after data is sorted by SUBJID. Starting with PP	
TOXTYPE	This variable is created to separate out Grade 1 toxicity from Grade 2 and higher.	1,2	2 separate datasets with one line per subject: TOXTYPE = 1 for 1 st occurrence of corneal event (CQ01NAM = Corneal Event). If CQ01NAM = missing, add 1 line for that subject. TOXTYPE = 2 for 1 st occurrence of corneal event (CQ01NAM = Corneal Event) with AETOXGRN ≥ 2. If CQ01NAM = missing, add 1 line for that subject. After these 2 datasets are complete, merge them.	adae
CORTOX	Presence or Absence of Corneal toxicity	0 or 1	When CQ01NAM = "Corneal Event", then CORTOX=1. When CQ01NAM =missing, then CORTOX=0.	adae
AETOXGRN	Standard Toxicity Grade	0,1,2,3		adae
TTECORTOX	Time to corneal toxicity event (day)		
 For TOXTYPE = 1 and CORTOX = 1, then TTECORTOX = AESTDY When TOXTYPE = 1 and CORTOX = 0, then TTECORTOX = (TRTSDT, LSTCTDT is coming from adsl dataset) For TOXTYPE = 2 and CORTOX = 1, then 	adae, adsl

Column Header	Data Item	Codes	Derivation/Comments	Source data set
			TTECORTOX = AESTDY 
 When TOXTYPE = 2 and CORTOX=0, then TTECORTOX = LSTCTDT – TRTSDT+ 1 	
DOAE	Duration of adverse event (days)		
 When CQ01NAM = Corneal Event and AONGO=N and AENDT= blank, then DOAE = ADURN; When CQ01NAM = Corneal Event and AONGO = N and AENDT= D, then DOAE = -99; When CQ01NAM = Corneal Event and AONGO=Y, then DOAE = LSTCTDT – AESTDY + 1; When CQ01NAM = missing, then DOAE = 0; 	adae, adsl
DOAECFLCD	DOAE Censoring Flag Code	0 or 1	When AONGO=N, then DOAECFLCD=0 When AONGO=Y, then DOAECFLCD=1	adae
LNDOAE	Log of duration of adverse event		LNDOAE = Log(DOAE); When DOAE=-99, LNDOAE =-99; When DOAE=0, LNDOAE=0	adae
CUMAMTCT	Cumulative dose to TTECORTOX (mg)		For corneal toxicity that occurred on dosing days, the dose on the corneal toxicity day was not included in the cumulative dose calculation.	adex. adae
Q4CUMAMTCT	Quartile of CUMAMTCT	0,1,2,3		derived
Q5CUMAMTCT	Quintile of CUMAMTCT	0,1,2,3,4		derived
CUMAUCCT	Cumulative AUC to TTECORTOX (ug.day/mL)		(Cumulative dose to TTECORTOX)/Individual Clearance of ADC	popPK output, adae
Q4CUMAUCCT	Quartile of CUMAUCCT	0,1,2,3		derived
Q5CUMAUCCT	Quintile of CUMAUCCT	0,1,2,3,4		derived
TAAUCCT	Time-average AUC till TTECORTOX (AUC/day)		The area under the plasma ADC concentration–time curve (AUC) per day (AUC/day) will be derived for each patient using the available ADC dosing information, individual patient oral clearance (CL/F) values from the population pharmacokinetic model, and the time to the occurrence of the corneal toxicity.	popPK output, adae
Q4TAAUCCT	Quartile of TAAUCCT	0,1,2,3		derived
Q5TAAUCCT	Quintile of TAAUCCT	0,1,2,3,4		derived
CANCER	Cancer type	0 or 1	0=Multiple Myeloma, 1=BCMA positive Lymphomas If TRT01AN = 12, then CANCER=1, else	adsl

Column Header	Data Item	Codes	Derivation/Comments	Source data set
			CANCER=0	
AMT	Amount (in mg) of GSK2857916 given in first cycle		AMT = AVAL when PARAMCD=ALTDOS and AVISIT=CYCLE 1 DAY 1	adex
Q4AMT	Quartile of AMT	0,1,2,3		derived
Q5AMT	Quintile of AMT	0,1,2,3,4		derived
TOTAMT	Total dose received (mg)		TOTAMT = AVAL * WEIGHTBL; Get AVAL for PARAMCD=CUMDOSE	adex,adsl
Q4TOTAMT	Quartile of TOTAMT	0,1,2,3		derived
Q5TOTAMT	Quintile of TOTAMT	0,1,2,3,4		derived
IDOSE	GSK2857916 initial cycle dose (mg/kg)	>0	IDOSE=adex.TRT01A; strip off units	adex
Q4IDOSE	Quartile of IDOSE	0,1,2,3		derived
Q5IDOSE	Quintile of IDOSE	0,1,2,3,4		derived
CMAx	First dose Cmax of ADC – Observed EOI on Cycle 1 (ng/mL)			popPK output
Q4CMAx	Quartile of CMAx	0,1,2,3		derived
Q5CMAx	Quintile of CMAx	0,1,2,3,4		derived
MMAFCMAx	First dose Cmax of MMAF – Observed EOI on Cycle 1 (ng/mL)			popPK output
Q4MMAFCMAx	Quartile of MMAFCMAx	0,1,2,3		derived
Q5MMAFCMAx	Quintile of MMAFCMAx	0,1,2,3,4		derived
CTAU	First dose C _{tau} of ADC– Observed pre-dose on Cycle 2			popPK output
Q4CTAU	Quartile of CTAU	0,1,2,3		derived
Q5CTAU	Quintile of CTAU	0,1,2,3,4		derived
AUC	First dose AUC(0-inf) of ADC (ug.day/mL)		First dose (mg)/Individual Clearance of ADC	popPK output
Q4AUC	Quartile of AUC	0,1,2,3		derived
Q5AUC	Quintile of AUC	0,1,2,3,4		derived
TOTAUC	Total AUC (ug.day/mL)		(Total dose received)/Individual Clearance of ADC	popPK output
Q4TOTAUC	Quartile of TOTAUC	0,1,2,3		derived
Q5TOTAUC	Quintile of TOTAUC	0,1,2,3,4		derived
MMAFAUC	First dose AUC(0-inf) of MMAF (ug.day/mL)		First dose (mg)/Individual Clearance of MMAF	popPK output
Q4MMAFAUC	Quartile of MMAFAUC	0,1,2,3		derived
Q5MMAFAUC	Quintile of MMAFAUC	0,1,2,3,4		derived
MMAFTOTAUC	Total AUC (ug.day/mL)		(Total dose received)/Individual Clearance of MMAF	popPK output
Q4MMAFTOTAUC	Quartile of MMAFTOTAUC	0,1,2,3		derived
Q5MMAFTOTAUC	Quintile of MMAFTOTAUC	0,1,2,3,4		derived

For efficacy

Column Header	Data Item	Codes	Derivation/Comments	Source data set
C	Exclusion identifier	Row Number DORDM	Set to line/row number unless one or more of the following conditions are met, then set to code: 
 DORDM: If DORD is missing 	adtte
STUDY	Study ID		1 = BMA117159	adsl
SUBJID	Subject identifier from source data		SUBJID = SUBJID	adsl
ID	NONMEM subject identifier		Sequential subject identifier across studies after data is sorted by SUBJID. Starting with P	derived
PFSCFLCD	PFS Censoring Flag Code	0 or 1	For PARAMCD=PFS_D, CNSR value is assigned to PFSCFLCD 0=Event 1=Censor	adtte
PFSD	PFS (Days)		For PARAMCD=PFS_D, AVAL value is assigned to PFSD	adtte
PFSM	PFS (Months)		For PARAMCD=PFS_M, AVAL value is assigned to PFSM	adtte
PFSY	PFS (Years)		For PARAMCD=PFS_D, (AVAL/365) value is assigned to PFSY	derived
TTRCFLCD	TTR Censoring Flag Code	0 or 1	For PARAMCD=TTR_D, Assign 1 to TTRCFLCD. For subjects where TTR_D is missing, assign 0 to TTRCFLCD.	adtte
TTRD	TTR (Days)		For PARAMCD=TTR_D, AVAL value is assigned to TTRD. For subjects where TTR_D is missing, assign PFSD to TTRD.	adtte
TTRM	TTR (Months)		For PARAMCD=TTR_M, AVAL value is assigned to TTRM. For subjects where TTR_M is missing, assign PFSM to TTRM.	adtte
TTRY	TTR (Years)		For PARAMCD=TTR_D, (AVAL/365) value is assigned to TTRY. For subjects where TTR_D is missing, assign PFSY to TTRY.	derived
DORCFLCD	DOR Censoring Flag Code	0 or 1	For PARAMCD=DOR_D, CNSR value is assigned to DORCFLCD 0=Event 1=Censor Assign "." for missing.	adtte
DORD	DOR (Days)		For PARAMCD=DOR_D, AVAL value is assigned to DORD. For subjects where DOR_D is missing, assign "."	adtte

Column Header	Data Item	Codes	Derivation/Comments	Source data set
DORM	DOR (Months)		For PARAMCD=DOR_M, AVAL value is assigned to DORM. For subjects where DOR_M is missing, assign “.”	adtte
DORY	DOR (Years)		For PARAMCD=DOR_D, (AVAL/365) value is assigned to DORY. For subjects where DOR_Y is missing, assign “.”	derived
ORDRESP		0,1,2,3,4,5,6	For PARAMCD=BCRSP, assign 0 for PD 1 for SD 2 for MR 3 for PR 4 for VGPR 5 for CR 6 for sCR	adrs
MAXPRED			Obtain AVAL for PARAMCD=MAXPRED. When AVAL is missing, MAXPRED = -999	adrs
RESPRATIO	Transform MAXRED to a ratio to baseline		
RESPRATIO = $\max((100+\text{MAXPRED})/100, 0.001)$
 
 When MAXRED is missing, MAXRED = -999 and RESPRATIO = -99 When MAXRED is less than -100 e.g. -100.15, RESPRATIO = negative (It is negative but greater than -8.99), then update RESPRATIO = 0.001 When MAXRED is equal to -100, RESPRATIO = 0, then update RESPRATIO = 0.001 	adrs, derived
RSPTYP	Response Type	1,2,3	1 for Serum M-Protein 2 for Serum FLC 3 for Urine M-Protein	adrs
CUMAMTP	Cumulative dose to PFS (mg)		For progression that occurred on dosing days, the dose on the progression day was not included in the cumulative dose calculation.	adex, adtte
Q4CUMAMTP	Quartile of CUMAMTP	0,1,2,3		derived
Q5CUMAMT	Quintile of CUMAMTP	0,1,2,3,4		derived
CUMAUCP	Cumulative AUC to progression (ug.day/mL)		(Cumulative dose to progression)/Individual Clearance of ADC	popPK output, adtte
Q4CUMAUCP	Quartile of CUMAUCP	0,1,2,3		derived
Q5CUMAUCP	Quintile of	0,1,2,3,4		derived

Column Header	Data Item	Codes	Derivation/Comments	Source data set
	CUMAUCP			
TAAUCP	Time-average AUC till progression (AUC/day)		The area under the plasma ADC concentration–time curve (AUC) per day (AUC/day) will be derived for each patient using the available ADC dosing information, individual patient oral clearance (CL/F) values from the population pharmacokinetic model, and the time to the occurrence of the PFS	popPK output, adtte
Q4TAAUCP	Quartile of TAAUCP	0,1,2,3		derived
Q5TAAUCP	Quintile of TAAUCP	0,1,2,3,4		derived
CUMAMTR	Cumulative dose to Response (mg)		For response that occurred on dosing days, the dose on the response day was not included in the cumulative dose calculation.	adex, adtte
Q4CUMTAMTR	Quartile of CUMAMTR	0,1,2,3		derived
Q5CUMTAMTR	Quintile of CUMAMTR	0,1,2,3,4		derived
CUMAUCR	Cumulative AUC to response (ug.day/mL)		(Cumulative dose to response)/Individual Clearance of ADC	adex, adtte, popPK output
Q4CUMAUCR	Quartile of CUMAUCR	0,1,2,3		derived
Q5CUMAUCR	Quintile of CUMAUCR	0,1,2,3,4		derived
TAAUCR	Time-average AUC till response (AUC/day)		The area under the plasma ADC concentration–time curve (AUC) per day (AUC/day) will be derived for each patient using the available ADC dosing information, individual patient oral clearance (CL/F) values from the population pharmacokinetic model, and the time to the occurrence of the response	popPK output, adtte
Q4TAAUCR	Quartile of TAAUCR	0,1,2,3		derived
Q5TAAUCR	Quintile of TAAUCR	0,1,2,3,4		derived
CUMAMTD	Cumulative dose to DOR (mg)		For DOR that occurred on dosing days, the dose on the DOR day was not included in the cumulative dose calculation.	adex, adtte
Q4CUMTAMTD	Quartile of CUMAMTD	0,1,2,3		derived
Q5CUMTAMTD	Quintile of CUMAMTD	0,1,2,3,4		derived
CUMAUCD	Cumulative AUC to DOR (ug.day/mL)		(Cumulative dose to DOR)/Individual Clearance of ADC	adex,adtte,popPK output
Q4CUMAUCD	Quartile of CUMAUCD	0,1,2,3		derived

Column Header	Data Item	Codes	Derivation/Comments	Source data set
Q5CUMAUCD	Quintile of CUMAUCD	0,1,2,3,4		derived
TAAUCD	Time-average AUC till DOR (AUC/day)		The area under the plasma ADC concentration–time curve (AUC) per day (AUC/day) will be derived for each patient using the available ADC dosing information, individual patient oral clearance (CL/F) values from the population pharmacokinetic model, and the time to the occurrence of the duration of response	adtte, popPK output
Q4TAAUCD	Quartile of TAAUCD	0,1,2,3		derived
Q5TAAUCD	Quintile of TAAUCD	0,1,2,3,4		derived
CANCER	Cancer type	0 or 1	0=Multiple Myeloma, 1=BCMA positive Lymphomas If TRT01AN = 12, then CANCER=1, else CANCER=0	adsl
AMT	Amount (in mg) of GSK2857916 given in first cycle		AMT = AVAL when PARAMCD=AL TDOSE and AVISIT= CYCLE 1 DAY 1	adex
Q4AMT	Quartile of AMT	0,1,2,3		derived
Q5AMT	Quintile of AMT	0,1,2,3,4		derived
TOTAMT	Total dose received (mg)		TOTAMT = AVAL* WEIGHTBL; Get AVAL for PARAMCD=CUMDOSE	adex,adsl
Q4TOTAMT	Quartile of TOTAMT	0,1,2,3		derived
Q5TOTAMT	Quintile of TOTAMT	0,1,2,3,4		derived
IDOSE	GSK2857916 initial cycle dose (mg/kg)	>0	IDOSE=adex.TR01A; strip off units	adex
Q4IDOSE	Quartile of IDOSE	0,1,2,3		derived
Q5IDOSE	Quintile of IDOSE	0,1,2,3,4		derived
CMAX	First dose Cmax of ADC – Observed EOI on Cycle 1 (ng/mL)			popPK output
Q4CMAX	Quartile of CMAX	0,1,2,3		derived
Q5CMAX	Quintile of CMAX	0,1,2,3,4		derived
MMAFCMAX	First dose Cmax of MMAF – Observed EOI on Cycle 1 (ng/mL)			popPK output
Q4MMAFCMAX	Quartile of MMAFCMAX	0,1,2,3		derived
Q5MMAFCMAX	Quintile of	0,1,2,3,4		derived

Column Header	Data Item	Codes	Derivation/Comments	Source data set
	MMAFCMAX			
CTAU	First dose C_{tau} of ADC– Observed pre-dose on Cycle 2			popPK output
Q4CTAU	Quartile of CTAU	0,1,2,3		derived
Q5CTAU	Quintile of CTAU	0,1,2,3,4		derived
AUC	First dose AUC(0-inf) of ADC (ug.day/mL)		First dose (mg)/Individual Clearance of ADC	popPK output
Q4AUC	Quartile of AUC	0,1,2,3		derived
Q5AUC	Quintile of AUC	0,1,2,3,4		derived
TOTAUC	Total AUC (ug.day/mL)		(Total dose received)/Individual Clearance of ADC	popPK output
Q4TOTAUC	Quartile of TOTAUC	0,1,2,3		derived
Q5TOTAUC	Quintile of TOTAUC	0,1,2,3,4		derived
MMAFAUC	First dose AUC(0-inf) of MMAF (ug.day/mL)		First dose (mg)/Individual Clearance of MMAF	popPK output
Q4MMAFAUC	Quartile of MMAFAUC	0,1,2,3		derived
Q5MMAFAUC	Quintile of MMAFAUC	0,1,2,3,4		derived
MMAFTOTAUC	Total AUC (ug.day/mL)		(Total dose received)/Individual Clearance of MMAF	popPK output
Q4MMAFTOTAUC	Quartile of MMAFTOTAUC	0,1,2,3		derived
Q5MMAFTOTAUC	Quintile of MMAFTOTAUC	0,1,2,3,4		derived

